1. STUDY SUMMARY

TITLE	Blood Biomarkers to improve management of mild traumatic BRAIN Injury implementation study
RUNNING TITTLE	BRAINI2 Implementation study
GENERAL OBJECTIVE	To assess the applicability and added value of a new clinical management pathway for patients with mild TBI presenting to the emergency department (ER), including the use of an in vitro diagnostic assay measuring the biomarkers GFAP and UCH-L1 in the serum, within the first 12 hours post-injury, to rule out the need for CT scan in mild TBI patients.
PRINCIPAL OBJECTIVE	
 
1) To evaluate the diagnostic performance of the VIDAS TBI (GFAP&UCH-L1) test in determining the need for CT-scan in patients with mild TBI admitted to the ER of Hospital 12 de Octubre.
 
2) To determine the safety of a management protocol including the use of the VIDAS GFAP&UCH-L1 test for patients with mTBI, in terms of complications or unforeseen neurological deterioration following the injury.
 
3) To estimate the reduction of CTs achieved using the biomarker test, by comparison with the management of TBI during the six months preceding the study (reference pathway).
 

PRINCIPAL OUTCOME	
Abnormal CT scan at admission in the ER
 
Deterioration: need for hospital admission or surgery due to TBI in the first week after TBI
 
Number of CTs prescribed in the management of mild TBI patients in the ER

PRINCIPAL OUTCOME MEASURES	
 
1) Diagnostic performance of the biomarker test
 
2) Proportion (%) of neurologic deterioration within 1 week post-TBI
 
3) Proportion (%) of CT scan prescribed in the ER over the period of the study for patients with mTBI
 

SECONDARY OBJECTIVES	
 
2.1) To determine the different times involved in the management of mild TBI patients and the effect of using the combined VIDAS test.
 
2.2) To establish differences in direct costs in the management of mild TBI in Hospital 12 de Octubre.
 
2.3.) To assess the compliance of physicians to the proposed algorithm.
 

SECONDARY OUTCOMES	
 
2.1) Time from admission to discharge. Time from admission to sample obtention. Time from venipuncture to availability of biomarker results.
 
2.2) Directs costs associated with mTBI management in the ER.
 
2.3.) Compliance with proposed algorithm.
 

SECONDARY OUTCOME MEASURES	
 
2.1) Time differences with respect to reference group
 
2.2) Cost difference comparing before and after the implantation of the biomarker test.
 
2.3) Proportion (%) of cases in which management follow the proposed algorithm
 

METHODOLOGY	
The study will compare the different outcome measures between a historic group obtained 6 months before the initiation of the new management protocol and the group of patients admitted in the ER with a diagnosis of a mTBI after the initiation of the new bundle of care.
 
The combined GFAP&UCH-L1 test has been included in the new bundle of care of mTBI for the management in the ER of all patients with mTBI. In summary the test will be performed to all patients with mTBI admitted to the ER of Hospital 12 de Octubre and included in the new management pathway of patients with mTBI incorporated in our hospital. All patients suffering a mTBI(GCS 15-13) and admitted within 12 hours of the TBI will be included in this pathway. If the patient is included in this pathway, the prescription of cranial CT will be performed following the results of the VIDAS TBI test if the patient has had a significant TBI and a GCS of 14 or 15. Those patients with GCS of 13 or a focal neurological deficit will receive both biomarkers and CT for their management during the study period. The VIDAS TBI test interpretation as defined by the manufacturer, bioMérieux, takes into account the responses of the two biomarkers: the VIDAS TBI test is negative if the two markers GFAP and UCH-L1 are negative (below the previously defined threshold concentration for each of the biomarkers). The test is positive if at least one of the two GFAP or UCH-L1 biomarkers is positive (beyond the threshold concentration). This test is already CE marked and has already been tested on a large number of European patients and has demonstrated good safety and reliability profiles.

STUDY TYPE	Protocol evaluation Implementation Study
STUDY DESIGN	Implementation study with prospective data collection with a control reference historic group
STUDY POPULATION	Mild TBI patients with significant brain trauma admitted in the ER of Hospital 12 de Octubre
INCLUSION CRITERIA	
-All adult patients suffering mild TBI:( Defined by at least criterion a) and d) and one or more of the other criteria)
 
    a) The presence of a plausible traumatic mechanism observed/or related by the patient's recount of the injury event.
 
    b) Presence of one or more clinical signs attributable to brain injury: Loss of consciousness immediately following injury, alteration of mental status immediately following the injury, posttraumatic amnesia or any neurological abnormality.
 
    c) At least two acute symptoms related to the injury: feeling confused or disoriented, headache, nausea, vomiting, dizziness, vision problems, memory problems, emotional lability or irritability.
 
    d) a GCS between 15 and 13, at least 30 minutes after injury.
 
-Blood sample obtained ≤12 h after injury and ideally before any imaging prescription.

EXCLUSION CRITERIA	
 
· GCS 3-12 on admission
 
· Age Below 18 years
 
· Time of injury unknown
 
· Time to injury exceeding 12 hours
 

BRAINI2-IMPLEMENTATION STUDY

	
 
· Primary admission for non-traumatic neurological disorder (e.g., stroke, spontaneous, intracranial hematoma)
 
· Penetrating head trauma
 
· Patient with mechanical ventilation from the trauma scene or prehospital management
 
· Venipuncture not feasible
 

NUMBER OF SUBJECTS	The implementation study will last for 6 months. The number of patients that are normally treated for this pathology is around 3000 patients each year. During the 6 months of the study around 1000 patients will at least be triaged for mild TBI
STUDY CENTRES	Hospital 12 de Octubre
PROVISIONAL CALENDAR OF THE STUDY	
 
- Start of inclusions: Jan 2025
 
- Inclusion period: 6 months
 
- End of inclusions: July 2025
 
- Length of participation of each subject: 2 weeks
 
- Total length of the study: 6 months
 

STATISTICAL ANALYSIS	
Outcome assessment
 
CT scan status will be attributed to each study participant based on the presence of intracranial lesions. Local CT reading will be used.
 
Outcome assessors will be blind to the participant biomarker status.
 
Quality control outcome assessment will be performed over the study period via sequential intra/inter observer agreement assessment.

EXPECTED IMPACT	This study will demonstrate the feasibility of using a bundle of care based on the determination of blood-based brain biomarkers in the management of patients with mTBI, in a real-life setting. It will also determine the time needed for obtaining results of these blood derived biomarkers and if there is reduction in associated cost and CT prescription related to its use.

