## BRAINI2-IMPLEMENTATION STUDY

Patients with mTBI lesions are often hospitalised in the standard ward where neurological monitoring consists of repeated CT scanning and clinical exams. Patients without lesions on the initial head CT-scan are also hospitalised when their GCS score after CT scan is less than 15.

Additionally, elderly patients on anticoagulants or antithrombotic drugs are more frequently hospitalised due to physicians' concerns about potential deterioration. This determines a bigger number of unneeded hospitalisations for these patients.

Therefore, although CT scan plays a pivotal role in the management of mTBI, there is an unmet clinical need for an objective tool to optimize and guide indications for CT scan, reduce clinical practice variability, reduce patient radiation exposure and improve patient outcome prediction.

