## BRAINII2-IMPLEMENTATION STUDY

positive (beyond the threshold concentration). This test has been already tested in a large number of European patients and has presented good safety and reliability profiles.

To determine the safety of the new protocol all information regarding the neurological status of the patients in relation to mTBI will be analyzed up to two weeks after the mTBI, specifically neurological deterioration, need for further observation of the patient or admission or need for treatment(medical or surgical) related to mTBI.

In order to determine the reduction of CT scans obtained with this new protocol, absolute numbers and proportions of patients finally scanned using this new protocol will be compared to the reference management of a similar number of patients during a similar historical period(i.e. data from the previous six month for patients attended for mTBI at Hospital 12 de Octubre).

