### 5.3.3. DATA COLLECTION AND DATA MONITORING

Data obtained as standard of care for the management of mTBI will be collected in the electronic clinical records. The Electronic Health Record is an essential tool for clinical decision-making and data collection, as it enables accurate and systematic documentation of patient information. However, its full potential is exploitable and useful when the data is structured. For this reason, and since the TBI information will be collected in the HER(Electronic Health Record), the hospital's IT data area improved the structuring and standardization of the information in the EHR. To this end, the mTBI diagnostic code was unified and codified (SNOMED CT) and a form was created with the questions that are asked when attending a patient with TBI. The completeness of the defined diagnosis together with the designed form will allow the identification of the cohort of patients with mTBI. In addition to the data included in the form, the study will collect demographic and baseline information at admission, the reason to prescribe brain CT scan and immediate CT findings by the local radiologist, biological data if indicated by the in-charge physician.

At 10 days postTBI, clinical research associates will review all information regarding the neurological status of the patients and the need for hospitalisation or other contacts to the ER in relation to mTBI. This review will be done thanks to the previous automatic extraction of the mTBI data collected in the EHR.

Regular quality checks on the information consigned in the EHR by attending physicians will be performed as a program for quality improvement of mTBI bundle. This program has been already run by the Department of Neurosurgery in order to enhance the recording of structured data in clinical records in our hospital. For this purpose, a dashboard in Power Business Intelligence (PowerBI) has been designed. In addition to functioning as an instrument for monitoring data recording, this PowerBi dashboard will also show the indicators outlined below for the purpose of protocol evaluation. These are time of care in the emergency department for patients with mTBI, percentage of CT requested, percentage of CT requested

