## BRAINII2-IMPLEMENTATION STUDY

in patients with negative biomarkers, percentage of CT requested in patients with positive biomarker, percentage of pathologic CT in patients with positive biomarker, percentage of pathologic CT in patients with negative biomarker, percentage of patients requiring admission and percentage of second ED visit after discharge.

Finally, the de-identified data from the mTBI cohort will be obtained and transferred into a web based electronic CRF(eCRF) built on RedCap to be able to be analysed. The database in RedCap will contain pseudo-anonymised clinical information about the patients with mTBI from six months prior to the implementation protocol and information from six months of the implementation protocol.

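### Principal outcome 3 (CT reduction) is CTs prescribed in the ER in the summary but patients scanned in section 3.2, and nothing says which is the principal estimate

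*Protocol*

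**What the plan says.** The CT reduction is the third of three principal objectives. Its outcome is worded in these places:

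- Protocol, section 1, principal outcome: "Number of CTs prescribed in the management of mild TBI patients in the ER".
- Protocol, section 1, principal outcome measures: "Proportion (%) of CT scan prescribed in the ER over the period of the study for patients with mTBI".
- Protocol, section 3.2: "absolute numbers and proportions of patients finally scanned using this new protocol will be compared to the reference management of a similar number of patients". The comparison period there is the previous six months.
- Protocol, section 5.3.3, dashboard indicators: "percentage of CT requested".

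Section 3.2 also explains how patients without a CT are handled in the diagnostic analysis. They count as CT negative unless they deteriorate or a later evaluation calls for a CT. A CT after the initial decision not to scan is thus expected for some patients.

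Follow-up lengths vary. Deterioration is counted over one week (section 1, principal outcomes; section 5.3.1). The record review is at 10 days (section 5.3.3), and participation lasts 10 days in section 11. Section 1 gives participation as two weeks, and section 3.2 follows safety for two weeks.

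**The concern.** A principal outcome should have one definition before the data are extracted. Here a reader can take the CT reduction to mean CTs ordered in the ER or patients who were scanned. Both could be computed from the same records with different results, and the choice could be made after both are known.

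The difference matters most for a rule-out test. Such a test can avoid a CT or merely postpone it. A measure that stops at the ER prescription may treat a postponed scan as an avoided one. A measure based on patients scanned, over a stated period, does not. Section 3.2 comes closer to this but gives no end date, so it does not settle which later scans count.

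**Working it through.** **No planned figure to reproduce.** Section 7.1 sizes the study on the negative predictive value. Its one directly checkable figure, 1000 × 10% = 100 CT-positive patients, reproduces but does not concern this outcome. No effect size, power or precision is stated for the CT reduction.

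**Definitions side by side.**

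| Place | Unit | Event | Setting | Time limit |
|---|---|---|---|---|
| Section 1, outcome | CTs (count) | prescribed | ER | none stated |
| Section 1, measure | CTs (%) | prescribed | ER | study period |
| Section 3.2 | patients (count and %) | scanned | none stated | none stated |
| Section 5.3.3, dashboard | CTs (%) | requested | none stated | none stated |

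**Cases the forms can treat differently.**

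1. A CT ordered before the test result and then cancelled counts as prescribed but not as scanned. Section 4.1 requires the blood sample before any imaging order, while the inclusion criteria in section 1 make this only an ideal.
2. A patient with two CTs can add two to a count of CTs but adds one to a count of patients.
3. A patient not scanned at first and scanned later on a ward counts in section 3.2 but not under the ER form. For a scan at a return visit to the ER, neither form says whether it belongs to the outcome.

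**Effect of late scans on the estimate.** Let R be the proportion of patients ever scanned and d the proportion whose only scan is not counted by the ER form. Assume that every ER prescription is carried out and count each patient once. The ER form then gives R − d in each period, and

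ER-form reduction = (R_ref − d_ref) − (R_new − d_new) = (R_ref − R_new) + (d_new − d_ref).

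The error is d_new − d_ref, the difference between the periods. It is zero if late scanning is equally common in both.

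**Size, by assumption only.** About 1000 tested patients is the protocol's figure (section 7.1). The other inputs are assumed: 300 of them leave the ER unscanned because of the test, 2% to 10% of these are scanned later and not counted, and d_ref = 0.

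- Low: 300 × 0.02 = 6 patients; 6 / 1000 = 0.6 percentage points.
- High: 300 × 0.10 = 30 patients; 30 / 1000 = 3.0 percentage points.

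If the true reduction were 10 points (for example, an assumed 70% falling to 60%), the ER form would read 10.6 to 13.0 points.

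**The case against.** **The count is not the only measure.** The summary lists an outcome and then its measure. For principal outcome 2 the event likewise becomes a percentage in the next row. Section 3.2 gives proportions as well. This stands. A reader might infer that a drop in patient volume could pass for a CT reduction, because a whole half-year of the stated 3000 to 3500 patients a year would be set against about 1000 tested. The documents do not support that reading: section 3.2 plans a similar number of reference patients, a proportion does not change with volume alone, and the 3500 are suspected TBI cases rather than tested patients.

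**Nothing describes a first CT postponed to the ward.** This also stands. A reader might take the background sentence that "neurological monitoring consists of repeated CT scanning and clinical exams" as evidence, but it concerns patients who already have lesions, so these are repeat scans. The support for later scans is the narrower exception in section 3.2.

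**Bias needs a difference between periods.** Sections 2.1 and following describe selective scanning under decision rules as current care, so late scans can occur in the reference period too. This makes the overstatement conditional; it does not remove the conflict of definitions.

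**Cancelled orders should be rare.** The pathway has the CT order follow the test result. That is fair, and no frequency is given, so nothing is claimed about their size.

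**Later contacts are already tracked.** The dashboard includes "percentage of patients requiring admission and percentage of second ED visit after discharge", and records are reviewed at 10 days. The data are therefore within reach, but no text links them to the CT outcome.

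**Extraction rules belong in the SAP.** Detailed rules may. A protocol that states one principal outcome in two incompatible ways is a different matter, and an SAP would have to depart from one of them.

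**Conclusion.** The concern holds as an inconsistency in a principal outcome. The summary measures CTs prescribed in the ER, section 3.2 measures patients scanned in any setting, and nothing ranks them. The ER-prescription form can also miss later scans that section 3.2 itself anticipates. If these are more frequent once the test is in use, that form overstates the reduction.

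The size of any overstatement is not known from the documents. The range of 0.6 to 3.0 percentage points rests wholly on the assumed 300 patients, the assumed 2-10%, no such scans in the reference period, and none of the late scans being counted by the ER form. No stated sample size or precision target is affected. The point is worth settling before extraction, as the correction is cheap and the figure answers one of the three principal objectives.

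**What to change.** In section 1 (principal outcome and outcome measure) and section 3.2, state one principal estimate in the same words: the proportion of eligible mTBI patients with at least one head CT performed for the injury at this hospital, whether in the ER, on a ward or at a return visit, from ER arrival to one stated follow-up day. Extract it in the same way for the reference and the test period.

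Choose the follow-up day and reconcile the one-week (sections 1 and 5.3.1), 10-day (sections 5.3.3 and 11) and two-week (sections 1 and 3.2) windows. The 10-day record review is already planned and could serve.

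Keep absolute numbers, and CTs prescribed or requested, as descriptive measures. State as a limitation that scans at other hospitals may not be captured, since electronic records are the only data source (section 5.1).

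The cost is protocol wording and one dated query of the hospital imaging record for both periods. Patient management does not change. The downside is that the reported reduction may be slightly smaller.

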## 4. STUDY DESIGN

### 4.1. STUDY OVERVIEW AND STUDY POPULATION

This is a single center study with prospective data collection with a control reference group.

Patients to be included in the new clinical pathway:

-Adult Patients ( $\geq 18$  years of age) suffering mild TBI:( Defined by at least criterion a) and e) and one or more of the other criteria)

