## BRAIN12-IMPLEMENTATION STUDY

- a) The presence of a plausible traumatic mechanism as described by the patient's recount of the injury event.
- b) Presence of one or more clinical signs attributable to brain injury: Loss of consciousness immediately following injury, alteration of mental status immediately following the injury, posttraumatic amnesia or any neurological abnormality.
- c) At least two acute symptoms related to the injury: feeling confused or disoriented, headache, nausea, vomiting, dizziness, vision problems, memory problems, emotional lability or irritability.
- e) GCS between 15 and 13, assessed at least 30 minutes after injury.

-Blood sample obtained ≤12 h after injury and before any imaging prescription.

Patients will not be included in the new pathway if:

- GCS 3-12 on admission
- Time of injury unknown
- Time to injury exceeding 12 hours
- Primary admission for non-traumatic neurological disorder (e.g., stroke, spontaneous, intracranial hematoma)
- Penetrating head trauma
- Patient with mechanical ventilation from the trauma scene or prehospital management.
- Venipuncture not feasible

Participation in the study will not affect patient management.

[figure not shown]

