### 5.3.2. Biological assessments (BA)

Blood samples will be drawn only for the management of patients with mTBI, as established by the mTBI care bundle and within 12 hours after TBI. The volume of blood collected will be that necessary to obtain results for both GFAP and UCH-L1 biomarkers. Permission for obtention of this blood sample will follow the normal standard of care of any other blood sample obtained in the ER. For normal health care management of patients admitted due to mild TBI in which a CT scan is going to be performed, laboratory analysis regarding hemogram and formula, coagulation status (Prothrombin time (PT), INR and aPTT) and conventional biochemistry analysis (Na, K, glycemia, creatinine, AST and ALT) are normally obtained by local laboratories as a standard of care. These data of the conventional laboratory analysis performed to these patients as standard of care will be obtained and stored in the eCRF.

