## 6. STUDY STOPPING RULES

### 6.1. STUDY STOPPING CRITERIA FOR A PARTICIPATING SUBJECT

Participants will be excluded from the study and replaced in case of a violation of an inclusion criterion, e.g. in the mTBI group: no mild TBI, no CT scan when the patient should have received one according to the study design, no blood sampling or after 12 hours post-injury.

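### The 12-hour limit runs to admission in one place and to the blood sample in others; the sample limit, with its exclude-and-replace rule, truncates three secondary time outcomes

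*Protocol*

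**What the plan says.** The protocol states the 12-hour limit with two different end points.

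- **To admission.** Study Summary, Methodology: "All patients suffering a mTBI(GCS 15-13) and admitted within 12 hours of the TBI will be included in this pathway".
- **To the blood sample.** Study Summary, Inclusion Criteria: "Blood sample obtained ≤12 h after injury and ideally before any imaging prescription". Section 4.1, under the lead-in "Patients to be included in the new clinical pathway", also requires "Blood sample obtained ≤12 h after injury". Section 5.3.2 has samples drawn "as established by the mTBI care bundle and within 12 hours after TBI".
- **Consequence of missing the sample limit.** Section 6.1 removes and replaces participants who violate an inclusion criterion, and gives as an example "no blood sampling or after 12 hours post-injury".
- **No end point named.** One exclusion criterion, in the Summary and in Section 4.1, sets a 12-hour limit counted from injury without saying to which event. It does not settle the matter.

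The secondary outcomes in the Summary include "Time from admission to sample obtention" and the interval from venipuncture to result. Section 3.3.1 adds, under a) and b), the intervals from injury to result and from admission to result.

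**The concern.** The Methodology sentence and the Section 4.1 list both govern entry to the same pathway, so they cannot be separated as a care rule and a study rule. A patient admitted 10 h after injury and sampled at 13 h is in under the first and out under the second.

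The sample limit also acts on an interval that the study wants to measure. Whether a patient stays in depends partly on how long that patient waited for the sample, and Section 6.1 then replaces those removed. No section asks for their number. The background section says that data are lacking on how long results take, and the Summary's expected impact promises to determine this. A patient who arrives in time but misses the sampling window is relevant to that question and drops out of sight.

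**Working it through.** No sample size, power or error rate in the protocol depends on this point, so there is no stated figure to reproduce. The check is one piece of logic and one illustration.

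**Logic.** Let A = injury to admission, S = admission to sample, R = sample to result.

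- Admission limit: keep if A ≤ 12 h.
- Sample limit: keep if A + S ≤ 12 h, that is S ≤ 12 − A.

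For a patient admitted at 10 h, S cannot exceed 12 − 10 = 2 h; for one admitted at 11 h, it cannot exceed 1 h. By outcome:

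- admission-to-sample = S: truncated at 12 − A;
- injury-to-result = A + S + R: its A + S part is capped at 12 h;
- admission-to-result = S + R: its S part is truncated;
- venipuncture-to-result = R: starts when the limit has already been met, so it is not truncated.

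At any given admission time the cut can only shorten S. For the pooled figures the direction also depends on how waits relate to arrival times; the illustration takes them as independent.

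**Illustration.** The protocol gives no time distributions, so these are assumptions: A lognormal, median 1.5, 3 or 5 h, log-SD 0.9; S lognormal, median 0.5, 1 or 2 h, log-SD 0.8; R lognormal, median 1 h, log-SD 0.4; all independent; 2 million draws per setting. Each pair shows admission-to-sample in hours under the admission limit, then under the sample limit. The percentage dropped is of patients admitted within 12 h.

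| Median A | Median S | Dropped | Mean S | Median S | 95th percentile of S |
|---|---|---|---|---|---|
| 1.5 | 0.5 | 0.2% | 0.69 → 0.69 | 0.50 → 0.50 | 1.87 → 1.86 |
| 1.5 | 1 | 0.8% | 1.38 → 1.35 | 1.00 → 0.99 | 3.73 → 3.63 |
| 1.5 | 2 | 3.6% | 2.76 → 2.47 | 2.00 → 1.94 | 7.46 → 6.37 |
| 3 | 0.5 | 1.0% | 0.69 → 0.68 | 0.50 → 0.50 | 1.87 → 1.84 |
| 3 | 1 | 2.5% | 1.38 → 1.32 | 1.00 → 0.98 | 3.74 → 3.52 |
| 3 | 2 | 7.5% | 2.76 → 2.37 | 2.00 → 1.88 | 7.47 → 5.97 |
| 5 | 0.5 | 2.2% | 0.69 → 0.67 | 0.50 → 0.49 | 1.87 → 1.81 |
| 5 | 1 | 5.0% | 1.38 → 1.28 | 1.00 → 0.97 | 3.73 → 3.39 |
| 5 | 2 | 12.3% | 2.75 → 2.27 | 2.00 → 1.82 | 7.45 → 5.61 |

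The largest fall in the mean is 2.75 − 2.27 = 0.48 h, and in the median 2.00 − 1.82 = 0.18 h. For the other intervals, mildest and strongest settings:

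- mean injury-to-result: 3.86 → 3.84 h and 8.58 → 7.56 h;
- mean admission-to-result: 1.77 → 1.77 h and 3.83 → 3.35 h;
- mean venipuncture-to-result: 1.08 h throughout.

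Among patients admitted 9 to 12 h after injury, 17% to 62% are dropped. If about 1000 patients were admitted in time (the number Section 7.1 expects to test), the dropped share would be 1000 × 0.002 = 2 to 1000 × 0.123 = 123 patients.

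**A second set of assumptions.** With A exponential (mean 2.5 to 4 h, arrivals within 12 h) and S lognormal (median 1 to 2 h, log-SD 0.8), the dropped share is 1.0% to 7.8%. Mean S moves from 1.38 to 1.34 h in the mildest setting and from 2.76 to 2.38 h in the strongest. With a median wait of 0.5 h in the same model, 0.3% to 1.1% are dropped and the mean falls by at most 0.01 h.

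**The case against.** **It is mainly one loose sentence.** Every operative rule uses the sample, and the Methodology sentence belongs to a narrative summary. The limits can also be read together: arrive within 12 h and be sampled within 12 h. This is fair as to how the study will probably run, and the sample limit agrees with the assay's use as described in Section 2.3. But that reading is exactly the one that truncates the time outcomes.

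**The rule does not select on delay in the emergency department.** A reader might infer that the slowest patients are removed. The documents do not support that. A patient arriving at 1 h who waits 10 h stays in (1 + 10 = 11 h), while one arriving at 11.5 h who waits 45 min goes out (12.25 h). In the exponential model with a 1 h median wait, 67–83% of those dropped arrived more than 8 h after injury, 29–41% had waited 2 h or less, and 82–90% of the slowest 5% of waits were kept. Only with a 2 h median wait is most of that slow tail lost (38–48% kept). This objection stands: the cut falls mainly on late arrivals.

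**The size may be negligible.** Section 5.2 has the test done on arrival, which points to short waits, and the larger figures need a 2 h median wait. The protocol does not say whether means, medians or percentiles will be reported. This also stands.

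**The consequence is limited.** These are secondary outcomes, and the biomarker intervals have no counterpart in a historical group that predates the test, so they are descriptive. True, but describing how long results take is a stated aim.

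**Analysis sets can be left to the SAP.** In general yes. Here the protocol itself fixes removal and replacement in Section 6.1, and an analysis plan cannot readily recover patients already removed under that rule.

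**Conclusion.** The inconsistency is in the text, concerns entry to one and the same pathway, and has to be reconciled. Under the sample limit, admission-to-sample, injury-to-result and admission-to-result are right-truncated, mainly among late arrivals, and their means and upper percentiles are biased toward shorter times.

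The size cannot be determined from the protocol. Over the assumed ranges, 0.2% to 12% of patients admitted in time are dropped, mean admission-to-sample is understated by 0 to about 0.5 h, and its 95th percentile by 0.01 h (1.87 to 1.86) to 1.84 h (7.45 to 5.61). Medians change little. These figures rest on lognormal times and on waits independent of arrival time.

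Two stronger conclusions are not supported. One is that every time-to-result outcome is cut short: venipuncture-to-result, the only time-to-result outcome listed in the Summary, is not. The other is that pathway entry ought to be redefined by arrival: that would choose a clinical rule, and nothing in this analysis bears on which rule is right. No effect on a primary outcome has been shown.

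**What to change.** Leave unchanged who is tested and how patients are managed, and amend the analysis populations.

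1. Reconcile the Summary (Methodology and Inclusion Criteria), Section 4.1, Section 5.3.2 and Section 6.1 so that the 12-hour limit has a stated end point in each. Name the end event in the exclusion criterion that lacks one.
2. Amend Section 6.1 so that patients admitted within 12 h of injury but sampled later, or not sampled, are not replaced.
3. Make a sample within 12 h a condition of the diagnostic-performance set only.
4. Keep late-sampled patients in the time outcomes. Patients never sampled have no biomarker interval and can only be counted.
5. Report the number admitted in time but sampled late, and the number not sampled. Show separately those for whom venipuncture was not feasible, which has its own exclusion criterion.

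The cost is a wording change and a little more analysis work, since Section 3.3.1 already takes the times from the hospital's systems. Reported times may come out slightly longer.
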